3 GENERAL STATISTICAL APPROACH

Two final analyses will be performed:

- One for the treatment phase: based on all patients and performed on data collected until the EoT visit (Week 16). This will be done once the last evaluable participant has completed his/her EoT visit.
- One for the follow-up period: based on all participants and all data.

The quantitative variables will be summarized using the following parameters:

- Number of non-missing data.
- Mean.
- Standard deviation (SD).
- Standard Error of the Mean (SEM).
- Median.
- Minimum.
- Maximum.

The qualitative variables will be summarized using the following parameters:

- Number of non-missing data,
- Counts and percentages.

Missing data or unknown responses will not be counted in the percentages.

The following definitions will be used in this document:

- Cohort: the study includes 2 cohorts: patients with moderate-to-severe AD cohort and a healthy volunteers cohort.
- Group: 3 groups are identified: patients' lesional skin area group, patients' non-lesional-skin area group, and healthy volunteers' normal skin group.

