4.3 STATISTICAL METHODS

All analysis variables will be described according to the methods defined in [Section 3](#) for the description of continuous and categorical variables.

The reporting of the efficacy and safety statistical analyses will be programmed according to the recommendations and templates of the BTD-009094 “Summarizing and reporting standard Early Development clinical trial data (except oncology)” Version 4.0 dated 02-Feb-2021.

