- As an exploratory analysis, the time to improvement of skin barrier function for lesional and non-lesional skin area measured by TEWL will be summarized for the treatment phase. Improvement is defined as time to the first post-baseline day for which at least 1 TEWL measure of a patient is equal or lower than the TEWL median in the matched healthy volunteers over time. Results might be reported through Kaplan-Meier plot in case of high number of events. Time to improvement of skin barrier function for lesional and non-lesional skin area will also be listed.

For the analyses of change (percent and absolute) from baseline in TEWL AUC (a composite measure before and after 5, 10, 15, and 20 STS) for skin barrier function in each skin group over time:

- As all TEWL values are expected to be positive, area under the TEWL curve will be calculated using the trapezoidal method over the 20 STS (measurement at every 5 STS and all other unplanned number of STS) at each visit. For AUC derivation only, TEWL data performed at unplanned number of STS will be used.
- Raw data and change (absolute and percent) from baseline will be summarized with descriptive statistics by skin group and timepoints. For follow-up period data, change from Week 16 (or last visit prior to use of rescue treatment) will also be reported.
- Box plots over time will be generated for absolute change from baseline/Week 16.
- As exploratory analysis, time to improvement of skin barrier function for lesional and non-lesional skin area measured by TEWL AUC will be summarized for the treatment phase. Improvement is defined as time to the first post-baseline day for which TEWL AUC of a patient is equal or lower than the median, of the corresponding TEWL AUC computed in his/her matched healthy volunteer over time. Results might be reported through Kaplan-Meier plot in case of high number of events.

TEWL conditions (ie, room temperature and humidity, etc.) will be summarized with descriptive statistics by timepoint.

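### Time to improvement has no rule for children who do not improve, and Kaplan-Meier is optional and tied to many events, when it is needed most with few

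*SAP*

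**What the plan says.** Section 4.3.3.2 contains two exploratory time-to-event analyses. For TEWL, "the time to improvement of skin barrier function for lesional and non-lesional skin area measured by TEWL will be summarized for the treatment phase". For the composite, "time to improvement of skin barrier function for lesional and non-lesional skin area measured by TEWL AUC will be summarized for the treatment phase". For TEWL the event is the "time to the first post-baseline day for which at least 1 TEWL measure of a patient is equal or lower" than the healthy-volunteer median; the AUC definition is parallel. Neither definition gives a value to a child who does not get there by Week 16.

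Both paragraphs end on the same option: "Results might be reported through Kaplan-Meier plot in case of high number of events". No threshold for a high number is given. Individual times are listed for TEWL; the AUC paragraph mentions no listing.

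The default comes from elsewhere. Section 4.3 states: "All analysis variables will be described according to the methods defined in" section 3. Section 3 says: "The quantitative variables will be summarized using the following parameters", and then lists number of non-missing data, mean, SD, SEM, median, minimum and maximum. No censoring rule appears anywhere in the SAP. Section 5.3 says only that imputation could be considered.

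**The concern.** A child who has not improved by Week 16 has no time to summarize. Under the section 3 default that child is a missing value and leaves the mean and median, so exclusion depends on the outcome itself. The same applies to a child who drops out before improving, whose later visits are removed from the mITT analysis after rescue (4.2.3), or whose later TEWL visits are removed after an impactful change of spot location (4.3.3.2).

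Kaplan-Meier handles such children properly, but the SAP makes it optional, limits it to a plot, and ties it to many events. With many events a plain summary does little harm. With few events most children are censored and the plain summary is least informative. The choice would also be made after the event count is known.

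At stake is the reading of how quickly lesional and non-lesional skin approach healthy skin. Two skin groups, or TEWL and TEWL AUC, could show similar times although quite different shares of children improved.

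**Working it through.** **Inputs from the SAP.** About 24 patients enrolled for 20 evaluable at 15% drop-out (1.3): 20 / 0.85 = 23.5, rounded up to 24, which reproduces the stated figure. Treatment phase of 16 weeks (1.4). STS weeks within it after baseline: 2, 4, 8, 12, 16 (Appendix B, footnote g).

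**Assumptions.** The SAP states no improvement rate or timing. TEWL visits are taken as Weeks 1, 2, 3, 4, 6, 8, 12 and 16, because the schedule table is partly broken in the text at hand. P is the share improving by Week 16.

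**Step 1: constant rate, expected values.** The cumulative share improved by week t is F(t) = 1 − (1 − P)^(t/16). The improver-only median is the first visit with F(t) ≥ P/2. The all-children median is the first visit with F(t) ≥ 50%.

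| P | P/2 | F(6) | F(8) | F(12) | Improver-only median (mean), weeks | All-children median |
|---|---|---|---|---|---|---|
| 25% | 12.5% | 10.2% | 13.4% | 19.4% | 8 (9.0) | not reached |
| 40% | 20% | 17.4% | 22.5% | 31.8% | 8 (8.6) | not reached |
| 50% | 25% | 22.9% | 29.3% | 40.5% | 8 (8.4) | Week 16 |
| 60% | 30% | 29.1% | 36.8% | 49.7% | 8 (8.0) | Week 16 |
| 75% | 37.5% | 40.5% | 50.0% | 64.6% | 6 (7.4) | Week 8 |

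At 75%, F(4) = 29.3%, so Week 6 is the first visit past half. On the AUC visits the improver-only median is also Week 8 from 25% to 60%.

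**Step 2: how firm this is with 20 children.** Simulating the same model with 20 children, the TEWL improver-only median has a 95% range of 2.5 to 16 weeks at P = 25%, and equals exactly 8 in about 15% of runs. At P = 60% the range is 3 to 12 weeks. The 8 weeks is a central tendency, not a prediction for one trial.

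**Step 3: other timing patterns.** 20 children, 4,000 runs per setting, TEWL visits. The average improver-only median (mean), in weeks, is:

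| Assumed timing | P = 10% | P = 30% | P = 50% | P = 80% |
|---|---|---|---|---|
| Equal chance at each visit | 6.1 (6.4) | 5.1 (6.1) | 4.3 (5.6) | 3.2 (4.5) |
| Constant rate in calendar time | 9.2 (9.1) | 8.8 (8.8) | 8.2 (8.4) | 6.2 (7.1) |
| Early responders | 4.3 (4.6) | 3.7 (4.5) | 3.5 (4.6) | 3.4 (4.6) |

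For AUC the improver-only mean runs from 5.2 to 9.7 weeks at 10% and from 5.2 to 7.7 at 80%.

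**Step 4: the same TEWL data by Kaplan-Meier, non-improvers censored at Week 16.** The median is not reached in essentially all runs at 10% and 20%, in 95% at 30%, in 40% to 42% at 50%, and in none at 80%. The mean time restricted to 16 weeks is 14.9 to 15.3 weeks at 10%, 12.6 to 13.9 at 30% and 6.8 to 8.9 at 80%. It therefore moves with the share improving, which the improver-only figure hardly does.

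**The case against.** The SAP nowhere says that non-improvers are dropped. Elsewhere for TEWL it usually spells out descriptive statistics, and the two time-to-improvement paragraphs omit those words. Time to improvement is also not among the variables listed in section 4.1. This stands in part: improver-only reporting is inferred from the default, and a reader who took it as a stated rule would go beyond the text. But 4.3 sends all analysis variables to section 3, and the SAP defines no other summary.

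The condition concerns a plot and does not forbid Kaplan-Meier estimates. That is true, but none are promised either.

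Non-improvement would be partly visible through the non-missing count and the TEWL listing. This stands too. Neither changes a mean or median computed on improvers, and no listing is stated for AUC.

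A reader might infer that the reported time will be half the true one or less, or will look fast however few respond. The documents do not support either. At 60% the all-children median falls on Week 16 only because 49.7% have improved by Week 12; the unrounded value is 12.1 weeks, and at 62% the visit-based median is Week 12. Under a constant rate the improver mean lengthens slightly as fewer improve (8.0 weeks at 60%, 9.0 at 25%), and 8 weeks is only the midpoint of the phase.

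Finally, the analysis is exploratory in an unpowered study. The main objective is served by the change-from-baseline analyses, so the consequence is limited.

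**Conclusion.** The concern holds in a limited form. The SAP leaves the handling of non-improvers, drop-outs and excluded visits undefined for both analyses. Its default would give an improver-only mean or median, and its condition withdraws the suitable method when most children are censored.

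The improver-only figure cannot exceed the Week 16 visit and says little about the share improving. Under an assumed constant rate its expected median is near 8 weeks from 25% to 60% improving, while the all-children median is not reached below 50%. Across the three timing patterns the average TEWL median is 4.3 to 9.2 weeks at 10% improving and 3.2 to 6.2 at 80%. All these sizes rest on assumed rates and timing, and a single trial of 20 children would vary widely around them. Primary and change-from-baseline results are not touched. The change should be made before reporting because it is cheap and needs no new data.

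**What to change.** In 4.3.3.2, for both TEWL and TEWL AUC:

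- Delete the event-count condition and use Kaplan-Meier whatever the number of events.
- Censor children who have not improved at their last evaluable treatment-phase TEWL assessment. In mITT, and where visits are removed for a location change, use the last visit before the excluded data.
- Report the number improved out of all children analysed, the cumulative proportion improved at each planned visit with 95% CI, and the median or 'not reached'.
- If a time among improvers is also shown, label it as such and print beside it the number improved out of the number analysed.

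The cost is SAP wording and one standard survival table for each measure, so a little more programming. The headline figure may become less favourable, since 'not reached' is likely if fewer than half improve.

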4.3.3.3 Analyses of tertiary/exploratory evaluation variables

The tertiary/exploratory endpoints will be analyzed on the mITT and ITT populations.

For the analysis of change (percent and absolute) from baseline in epidermal hypertrophy parameters and in stratum corneum lipid structure over time, raw data and change (absolute and percent) from baseline will be summarized with descriptive statistics by skin group and timepoint. For follow-up period data, change from Week 16 (or last visit prior to use of rescue treatment) will also be reported. Profiles over time will be generated for individual values and group means for raw data and absolute change from baseline.

For the analysis of the change (percent and absolute) from baseline in CDLQI, EASI, ISS for target lesion, POEM, assessment of worst itch NRS, sleep disturbance NRS, skin pain NRS, and photograph outputs (TiVi and skin roughness indexes) obtained from skin imaging over time, raw data and change (absolute and percent) from baseline will be summarized with descriptive statistics by skin group and timepoint. For follow-up period data, change from Week 16 (or last visit prior to use of rescue treatment) will also be reported. Profiles over time will be generated for individual values (spaghetti plot only for PRO measures [POEM, CDLQI, worst itch NRS, sleep disturbance NRS, and skin pain NRS]) and group means for raw data and absolute change from baseline (only for ClinROs measures [EASI and ISS]).

A correlation analysis will also be investigated between baseline values of TEWL (before and after each number of STS), and TEWL AUC in lesional and non-lesional skin of AD patients with the following baseline measures: EASI, targeted lesion ISS, image-derived severity score in targeted lesional skin, and quantified epidermal hypertrophy and structure changes in OCT and FTIR measures. For this analysis, scatterplot to visualize the form of the relationship between variables will be produced for patients' cohort at specific time points: baseline, Week 8, Week 16 and Week 28. Pearson correlation will be assessed at each defined time point for EASI, ISS, photograph outputs, OCT outputs: epidermal thickness, supervidial plexus depth, blood vessel diameter and density, and FTIR measures. Pearson correlation coefficient and p-value will be reported. Spearman's rank correlation will be assessed at each defined timepoint for ISS. Spearman correlation coefficient and p-value will be reported. As an exploratory analysis repeated measures correlation method might be used to assess the overall correlation pooling data from baseline, Week 8, Week 16 and Week 28 (3).

The same approach will be used to investigate the correlation between percent change from baseline in TEWL (before and after each number of STS), and TEWL AUC in lesional and non-lesional skin of AD patients at Week 8, Week 16 and Week 28 with corresponding change from baseline of the aforementioned measures (ie, EASI, targeted lesion ISS ...).

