1.3 DETERMINATION OF SAMPLE SIZE

No formal sample size calculation was performed for this exploratory study. It was based on medical/clinical judgment and is consistent with the sample size from similar studies in the literature (2).

Allowing for drop-out rate of 15%, a total of approximately 24 pediatric patients with moderate-to-severe AD will be enrolled to achieve 20 evaluable patients. An approximately equal number of age, gender, location of targeted lesion area and site matched healthy volunteers serving as a reference comparator cohort will be enrolled. Any drop-out healthy volunteer for whom the matched patient is considered as evaluable will not be replaced.

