4.3.3 Analyses of evaluation variables

4.3.3.1 *Analysis of main evaluation variable(s)*

The primary endpoint will be analyzed on the mITT population. As a sensitivity analysis, it will also be analyzed based on the ITT population.

The calculation of changes (absolute and percent) from baseline will be based on the same number of STS (ie, for absolute change from baseline after 5 STS at W16: Change TEWL at W16 after 5 STS = TEWL value at W16 after 5 STS – TEWL value at baseline after 5 STS).

If a change in spot anatomical location changed versus Day 1 is identified and assessed by the study team as having a significant impact on skin barrier, only visits prior to the location change will be considered in the statistical analysis of TEWL data. Raw data and change (absolute and percent) from baseline will be summarized with descriptive statistics by timepoint.

Profiles over time (from baseline to Week 16) will be generated for individual values (spaghetti plot).

For information purpose as study is not powered (no multiplicity correction will be applied):

- For each number of STS, the evolution of the percent change from baseline over time will be analyzed using a repeated measures analysis of variance with visit, type of skin, interaction between visit and type of skin, age, and baseline value as fixed effects and subject identifier as random effect, at a Type 1 error level of alpha=0.05. In case of heterogeneity at baseline, additional covariates (ie, site, race ...) could be added in this statistical model.
- The following covariance structures will be tested in the REPEATED statement of the PROC MIXED: un, vc and cs at least. The structure with the smallest Bayesian information criteria will be selected for the final model.
- Point estimate and two-sided 95% confidence interval and corresponding two-sided p-value will be reported for each effect. No comparison will be performed.
- If assumption of normal distribution is strongly violated, transformation method could be used: eg, log transformation; normality assumption will be assessed through quantile-quantile plot and Shapiro-Wilk test at 5% Type I error.

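### TEWL correlations with EASI, photograph, OCT and FTIR measures rest on Pearson's r only; with about 20 children, one outlying child can hide a real correlation, or create one if extreme on both measures

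*SAP*

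**What the plan says.** SAP Section 4.3.3.3 states "Pearson correlation will be assessed at each defined time point for EASI, ISS, photograph outputs, OCT outputs", and goes on to list the individual OCT outputs and the FTIR measures. For these, "Pearson correlation coefficient and p-value will be reported". Spearman's "rank correlation will be assessed at each defined timepoint for ISS", so ISS receives both coefficients and no other measure does. The section applies the same approach to percent change from baseline in TEWL and TEWL AUC at Weeks 8, 16 and 28.

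Scatterplots are planned at baseline and at Weeks 8, 16 and 28. A repeated measures correlation pooled over visits is optional and is not described as rank-based. For these correlations the section gives no transformation, outlier rule or leave-one-out check.

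On numbers, Section 1.3 says "No formal sample size calculation was performed for this exploratory study" and that "a total of approximately 24 pediatric patients with moderate-to-severe AD" "will be enrolled to achieve 20 evaluable patients".

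**The concern.** These coefficients are the SAP's committed numerical answer to its second exploratory objective: how barrier function measured by TEWL relates to disease severity, imaging and skin structure. Pearson's r is sensitive to single points, and with about 20 children one point carries a lot of weight. Percent change cannot fall below -100% but has no upper limit, so a large positive value from one child is possible. A scatterplot would show such a child, but nothing in the plan links the plot to the coefficient, and the reported r and p-value would still follow that child.

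Section 4.3.3.1 does foresee non-normal data for the primary endpoint: "If assumption of normal distribution is strongly violated, transformation method could be used". That provision belongs to the repeated measures model and does not extend to the correlations.

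**Working it through.** **Inputs.** From Section 1.3: 20 evaluable patients, about 24 enrolled, 15% dropout. Two-sided alpha 0.05 is assumed; the SAP states 0.05 for the mixed model and gives none for the correlations. The true correlations (0 and 0.6) and the outlier positions are also assumptions, so a range is shown. Positions are written TEWL/other measure, in SD units.

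**1. The plan's own figure.** 20/(1 - 0.15) = 23.5, rounded up to 24, as stated.

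**2. Critical value.** |r| = t/√(n - 2 + t²), with t the 97.5% point on n - 2 df. This gives 0.444 for n = 20 and 0.404 for n = 24.

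**3. Exact effect of one child.** Take 19 standardised pairs (sum of squares 18 on each axis, correlation r₀) and add one child at (k, j):

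r = (18r₀ + kj·19/20) / √[(18 + k²·19/20)(18 + j²·19/20)]

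- Hiding, r₀ = 0.60 (p = 0.007 in the 19). Child at +5/0: 10.8/√(41.75 × 18) = 0.39, p = 0.086. Child at +4/-2: (10.8 - 7.6)/√(33.2 × 21.8) = 0.12, p = 0.62.
- Creating, r₀ = 0. Child at +3/+3: 8.55/26.55 = 0.32, p = 0.17. At +4/+4: 15.2/33.2 = 0.46, p = 0.042. At +5/+5: 23.75/41.75 = 0.57, p = 0.009.
- TEWL extreme alone, r₀ = 0, child at +5/0: the numerator is 0, so r = 0.

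**4. Simulation.** 20,000 samples per setting: bivariate normal data with one child fixed at the stated position, and both coefficients compared with the critical |r| from step 2. Share of samples with p<0.05 at n = 20:

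| True correlation | Outlying child | Pearson | Spearman |
|---|---|---|---|
| 0.6 | none | 83.8% | 76.8% |
| 0.6 | +5/0 | 34.5% | 69.3% |
| 0.6 | +4/-2 | 1.0% | 28.4% |
| 0 | none | 4.9% | 4.8% |
| 0 | +5/0 | 0.3% | 4.1% |
| 0 | +5/+2 | 22.5% | 6.8% |
| 0 | +3/+3 | 26.5% | 6.9% |
| 0 | +4/+4 | 58.1% | 6.9% |
| 0 | +5/+5 | 87.1% | 7.2% |

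A repeat of the 0.6, +5/0 setting gave 33% and 69%, hence the quoted range of 33-35% for Pearson. At n = 24 the pattern is the same: 53.5% against 79.7% for 0.6 with +5/0, and 55.8% against 6.8% for 0 with +4/+4.

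**5. Skewness without an outlier.** With only TEWL percent change log-normal, true correlation 0.6 on the log scale and n = 20, Pearson against Spearman is 82.6% v 76.9% at log SD 0.3, 80.2% v 77.0% at 0.5, 74.9% v 77.1% at 0.8 and 70.4% v 77.4% at 1.0. Pearson is better at 0.3 and 0.5, and Spearman at 0.8 and 1.0. The case therefore rests on outlying children and not on skewness as such.

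**The case against.** The strongest reply is that the plan says nothing wrong here. Using a rank coefficient for ISS, an ordinal sum from 0 to 12, and Pearson's r for continuous measures is a conventional distinction. Scatterplots are the usual outlier check with about 20 points, and the results are shown for both the mITT and ITT populations. The endpoints are tertiary, and Section 5.6 sets no hypothesis tests in advance. In clean normal data Pearson has more power, and a rank coefficient answers a different question (monotone rather than linear association). All of this stands. It limits the weight of the point and argues for keeping Pearson's r. It does not remove the gap: for every measure but ISS, the number and p-value reported can be decided by one child.

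Two stronger readings are tempting. A reader might infer that one extreme percent change in TEWL can create a correlation. It cannot by itself: with true correlation 0, a child at +4 SD on TEWL with an ordinary value on the other measure gives p<0.05 in 4.9% of samples for either coefficient, and skewed TEWL (log SD 0.2 to 0.8) leaves Pearson's false-positive rate at 5.0-5.1%. A reader might also take the SAP's remarks on strong TEWL variability (Sections 4.3.2.2 and 4.3.3.2) as evidence that outlying children are expected. Those remarks concern differences between three adjacent spots measured before or without stripping, and explain why spots are not averaged. They say nothing about outlying children or about TEWL after stripping.

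**Conclusion.** The point holds as a minor improvement. It is not an error or a contradiction in the SAP. For EASI, photograph, OCT and FTIR measures, the plan commits to a single coefficient that one child in 20 to 24 can move across the conventional threshold. An extreme TEWL value alone lowers the chance of detecting a true correlation of 0.6 from about 84% to about a third. Spearman falls too, but only from 77% to 69%. A false correlation requires a child who is off-centre on both measures. Spearman lessens the problem without removing it: at +4/-2 it still falls to 28%.

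The sizes depend on the assumed outlier positions and true correlations, for which the SAP supplies no figures. Whether any child will lie that far out cannot be judged from the document.

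**What to change.** In Section 4.3.3.3, extend to every pair what is already planned for ISS: Spearman's coefficient and p-value beside Pearson's, at each time point and for the change-score correlations. State in the text wherever the two disagree and refer to the scatterplot. Do not make the rank coefficient decide the conclusion by default, because that would be a trade-off between linear and monotone association. A leave-one-out range for Pearson's r is a useful option. A 95% confidence interval could also be given, but it would be an addition, since none is planned for ISS. Settle this before the correlations are run, so that the choice of coefficient cannot follow the result.

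The cost is one more column in tables already planned, using a method the SAP already names. Spearman has about 7 points less power than Pearson in clean normal data (76.8% against 83.8% above), which is why Pearson's r stays.
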